### **Contraceptive Requirements**

Note that the drug-drug interaction of 731 and systemic (oral/injectable/implantable) hormonal birth control has not been assessed; therefore, systemic hormonal birth control is not considered an effective birth control method for female subjects for the purposes of this study.

Female subjects of childbearing potential (defined above) must agree to use dual effective birth control methods for the duration of the study including the follow-up period. Effective birth control methods include male or female condom (may not be used together due to increased risk of breakage), vasectomy, tubal sterilization, intrauterine device (IUD), diaphragm, or cervical cap. Female subjects must have a negative serum pregnancy test at Screening and a negative urine pregnancy test prior to receiving the first dose of study drug at Baseline (Day 1).

All male subjects must agree to use dual effective birth control methods with their female partners if they are of childbearing potential for the duration of the study including the follow-up period. In this case, effective birth control methods include systemic (oral/injectable/implantable) hormonal birth control, male or female condom (may not be used together due to increased risk of breakage), vasectomy, tubal sterilization, IUD, diaphragm, or cervical cap. Male subjects must avoid sperm donation from the time of the first dose of study drug and throughout the study period, and for at least 30 days after administration of the last dose of study drug.

## APPENDIX 5 CYTOCHROME P450 3A4 INHIBITORS AND INDUCERS AND CYP2C9 SUBSTRATES

The following drugs are known inhibitors of CYP3A4 and should be avoided when taking 731:

CYP3A4 Inhibitors	
HIV antivirals	indinavir, nelfinavir, ritonavir, saquinavir
Other	clarithromycin, itraconazole, ketoconazole, nefazodone, saquinavir, idelalisib, ribociclib, telithromycin, aprepitant, erythromycin, fluconazole, grapefruit, grapefruit juice, netupitant/palonosetron, verapamil, diltiazem, voriconazole cimetidine, amiodarone, NOT azithromycin, chloramphenicol, boceprevir, ciprofloxacin, delavirdine, diethyl-dithiocarbamate, fluvoxamine, gestodene, imatinib, mibepradil, mifepristone, norfloxacin, norfluoxetine, starfruit, telaprevir, voriconazole

The following drugs are known substrates of CYP2C9 and are prohibited or should be avoided when taking 731:

CYP2C9 Substrates	
Narrow therapeutic index substrates that are prohibited while taking 731	Warfarin, phenytoin
Substrates that should be avoided while taking 731	Amitriptyline, capecitabine, celecoxib, clopidogrel, diclofenac, doxepin, fluoxetine, Fluvastatin, glibenclamide, glimepiride, glipizide, glyburide, ibuprofen, irbesartan, lesinurad, lornoxicam, losartan, meloxicam, nateglinide, piroxicam, rosiglitazone, naproxen, suprofen, tamoxifen, tolbutamide, torsemide, valproic acid, venlafaxine, voriconazole, zafirlukast

The following drugs are known inducers of CYP3A4 and should be avoided when taking 731:

CYP3A4 Inducers	
Inducers that should be avoided while taking 731	Barbiturates, brigatinib, carbamazepine, efavirenz, enzalutamide, glucocorticoids, modafinil, nevirapine, oxcarbazepine, phenobarbital, phenytoin, pioglitazone, rifabutin, rifampin, st. john's wort, troglitazone

Abbreviations: 731 = ABI-H0731; CYP = cytochrome P450.

Source: The Flockhart Table. <http://medicine.iupui.edu/clinpharm/ddis/main-table#> (Accessed 6 March 2020).

Note: Refer to Exclusion Criterion #1, Section 5.3 of the protocol for prohibited medications. Additionally, the list of medications included in this appendix is not exhaustive. The Investigator should evaluate the mechanism of other concomitant medications to determine if they should be allowed in the study.

The details of prohibited concomitant medications and medications with a potential for drug-drug interactions with ETV and Peg-IFN $\alpha$  are described in the respective package inserts.

## LIST OF ABBREVIATIONS

---

AASLD	american association for the study of liver diseases
AE	adverse event

---

---

ALT	alanine aminotransferase
ANCOVA	analysis of covariance
ATC	anatomical therapeutic chemical
BLOQ	below the limit of quantitation
BMI	body mass index
cHBV	chronic hepatitis B virus infection
CI	confidence interval
CMH	Cochran-Mantel-Haenszel
CSR	clinical study report
DAIDS	Division of AIDS
DNA	deoxyribonucleic acid
DRC	data review committee
ECG	electrocardiogram
eCRF	case report form
EDC	electronic data capture
EOS	end of study
EOT	end of treatment
ET	early termination
ETV	entecavir
FAS	full analysis set
GT	genotype
Hb	hemoglobin
HBcrAb	antibody to the HBV core-related antigen
HBcrAg	hepatitis B core-related antigen
HBeAb	HBeAg antibody
HBeAg	hepatitis B “e” antigen
HBsAb	HBsAg antibody
HBsAg	hepatitis B surface antigen
HBV	hepatitis B virus
HLGT	high-level group term
HLT	high-level term
ID	identification
IFN $\alpha$	interferon alpha
INR	international normalized ratio
IPD	important protocol deviation(s)
IRT	interactive response technology
LLOQ	lower limit of quantitation
LLT	lower-level term
LOD	limit of detection
LOQ	limit of quantitation

---

---

MedDRA	medical dictionary for regulatory activities
MMRM	mixed model for repeated measures
NrtI	Nucleos(t)ide reverse transcriptase inhibitor
PD	protocol deviation(s)
Peg	pegylated
pgRNA	pregenomic ribonucleic acid
PK	pharmacokinetics
PT	preferred term
Q1, Q3	first quartile, third quartile
QD	once daily
RAV	resistance associated variants
SAE	serious adverse event
SAP	statistical analysis plan
SD	standard deviation
SE	standard error
SOC	system organ class
TEAE	treatment-emergent adverse event
TFLs	tables, figures, and listings
ULN	upper limit of normal
VBR	vebicorvir
WHO	world health organization

## 1. INTRODUCTION

Study ABI-H0731-203 is a randomized Phase 2a, multicenter, open-label study evaluating vebicorvir (VBR; formerly ABI-H0731) -containing regimens in subjects with chronic hepatitis B virus (HBV) infection (cHBV). The target population is male or female subjects, 18 to 65 years of age, inclusive, treatment naïve with hepatitis B virus “e” antigen (HBeAg) positive cHBV and no evidence of cirrhosis or end-stage liver disease.

This statistical analysis plan (SAP) describes the statistical analysis methods and data presentations to be used in tables, figures, and listings (TFLs) in the clinical study report (CSR) for Study ABI-H0731-203. This SAP is based on the study protocol amendment 3, dated 29 July 2021 and the electronic case report form (eCRF). In July 2022, Assembly made the decision to terminate this study and discontinue the development of VBR after review of interim data suggested that none of the study drug regimens were likely to lead to functional cure. Subsequently, participants in Study ABI-H0731-203 ended study treatment and entered in follow-up period with entecavir (ETV) for 12 weeks. . Therefore, only key safety and efficacy endpoints will be performed for this study. The SAP will be finalized before database lock. Any changes made after the finalization of the SAP will be documented in the Synoptic CSR.

### 1.1. Study Objectives

The primary objective of this study is as follows:

- To evaluate the safety and tolerability of VBR) when administered in combination with entecavir (ETV) with or without pegylated interferon alpha (Peg-IFN $\alpha$ ) in subjects with cHBV

The secondary objectives of this study are as follows:

- To evaluate the effect of VBR when administered in combination with ETV with or without Peg-IFN $\alpha$  in reducing HBV pgRNA levels in subjects with cHBV
- To evaluate the effect of VBR when administered in combination with ETV with or without Peg-IFN $\alpha$  in reducing HBV deoxyribonucleic acid (DNA) levels in subjects with cHBV
- To evaluate the effect of VBR when administered in combination with ETV with or without Peg-IFN $\alpha$  in reducing HBV antigens (ie, HBeAg, hepatitis B core-related antigen [HBcrAg], and hepatitis B surface antigen [HBsAg]) in subjects with cHBV
- To evaluate the effect of VBR when administered in combination with ETV with or without Peg-IFN $\alpha$  on normalization of alanine aminotransferase (ALT)
- To evaluate the pharmacokinetics (PK) of VBR and future PK evaluation of Peg-IFN $\alpha$  and ETV in subjects with cHBV
- To evaluate the emergence of resistance to VBR when administered with ETV with or without Peg-IFN $\alpha$

## 1.2. Study Design

[figure not shown]
This study will assess the safety, antiviral activity, and PK of VBR administered in combination with ETV with or without Peg-IFN $\alpha$  in treatment-naïve, HBeAg positive Chinese subjects with cHBV. The study will be conducted at approximately 5 to 10 study sites in China.

Approximately 60 eligible subjects with HBeAg positive cHBV will be randomly assigned in a 1:1:1 ratio to the treatment groups shown in the study overview presented in [Figure 1-1 Study Overview](#).

Treatment with VBR and/or ETV will be administered orally, once daily; treatment with Peg-IFN $\alpha$  will be administered subcutaneously, once weekly. Group 1 will receive VBR+ETV for 24 weeks, Group 2 will receive VBR+ETV+Peg-IFN $\alpha$  for 24 weeks and Group 3 will receive ETV+Peg-IFN $\alpha$  for 24 weeks. All subjects will receive VBR+ETV from Week 24 through Week 48 and then ETV alone from Week 48 through Week 60 during the 12-week follow-up period.

Treatment assignments will be stratified by the HBV genotype (GT; ie, GT A or B vs GT C or D, vs other GTs) and baseline ALT (ie, ALT  $<5 \times$  upper limit of normal [ULN] vs ALT  $\geq 5 \times$  ULN) during the Screening visits.

**Figure 1-1** Study Overview

Abbreviations: BL = Baseline; ETV = entecavir; Peg-IFN $\alpha$  = pegylated-interferon alpha; Wk = week.

Note: ABI-H0731 is the former designation for VBR.

The schedule of study procedures is presented in tabular form in Appendix 1 of the study protocol.

## 1.3. Sample Size and Power

Approximately 60 eligible male or female subjects between the ages of 18 and 65 years with HBeAg positive cHBV will be enrolled in the study. Subjects will be randomized to receive 1 of the following 3 treatments, VBR+ETV, ETV+Peg-IFN $\alpha$ , or VBR+ETV+Peg-IFN $\alpha$  in a 1:1:1 ratio.

This is a proof-of-concept study. The sample size is similar to that previously utilized for this type of study and is not based upon statistical considerations.

## **1.4. Methods of Assigning Subjects to Treatment**

### **1.4.1. Randomization**

Randomization of eligible subjects to their respective treatment assignments will be performed centrally using an Interactive Response Technology (IRT) system. The IRT system will assign eligible subjects in a 1:1:1 ratio to receive either VBR+ETV, VBR+ ETV+Peg-IFN $\alpha$  or ETV+Peg-IFN $\alpha$  for 24 weeks. Treatment assignments will be stratified by the HBV GT (ie, GT A or B vs GT C or D, vs other GTs) and baseline ALT (ie, ALT <5  $\times$  ULN vs  $\geq$ 5  $\times$  ULN) collected at Screening. Additional information on the use of the IRT is provided in the IRT User Manual.

### **1.4.2. Blinding**

Not applicable as this is an open-label study.

## **2. TYPE OF PLANNED ANALYSIS**

### **2.1. Interim Analyses**

No formal interim analyses are planned. As an open-label study, the data will be reviewed periodically.

### **2.2. Final Analysis**

As of 25 July 2022, the study was terminated early. The final analysis to support a ‘Synoptic Clinical Study Report’ will be performed after all subjects have discontinued or completed the 12-week follow-up visits, outstanding data queries have been resolved or adjudicated as unresolvable, and the data have been cleaned and finalized.

### **3. GENERAL CONSIDERATIONS FOR DATA ANALYSES**

Analysis results will be presented using descriptive statistics. For categorical variables, the number and percentage of subjects in each category will be presented; for continuous variables, the number of subjects (n), mean, standard deviation (SD) or standard error (SE), median, first quartile (Q1), third quartile (Q3), minimum, and maximum will be presented.

No formal inference is planned in this study. Hence no multiplicity adjustment is required.

#### **3.1. Analysis Sets**

Analysis sets define the subjects to be included in an analysis. Analysis sets and their definitions are provided in this section. The analysis set will be identified and included as a subtitle of each table, figure, and listing. For each analysis set, the number and percentage of subjects eligible for inclusion will be summarized by treatment group. A listing of reasons for exclusion from analysis sets will be provided by subject.

##### **3.1.1. All Randomized Analysis Set**

All Randomized Analysis Set includes all subjects who were randomized in the study, classified according to the treatment group into which they were randomized regardless of the actual treatment received.

##### **3.1.2. Full Analysis Set**

The Full Analysis Set (FAS) includes all randomized subjects, classified according to the treatment group into which they were randomized regardless of the actual treatment received who took at least 1 dose of study drug. This is the primary analysis set for efficacy analyses.

##### **3.1.3. Safety Analysis Set**

The Safety Analysis Set includes all subjects, classified according to the actual treatment received regardless of randomization assignment, who took at least 1 dose of study drug. This is the primary analysis set for safety analyses.

#### **3.2. Subject Grouping**

For analyses based on the All Randomized Analysis Set and FAS, subjects will be grouped according to the treatment to which they were randomized. For analyses based on the Safety Analysis Set, subjects will be grouped according to the actual treatment received. The actual treatment received will differ from the randomized treatment only when their actual treatment differs from randomized treatment for the entire treatment duration.

### **3.3. Strata and Covariates**

Subjects will be randomly assigned to treatment groups via an IRT system in a 1:1:1 ratio using a stratified randomization schedule. Stratification will be based on the following variables during the Screening visits:

- HBV GT (ie, GT A or B vs GT C or D, vs other GTs)
- Baseline ALT (ie, ALT  $<5 \times$  upper limit of normal ULN vs ALT  $\geq 5 \times$  ULN)

If there are discrepancies in stratification factor values between the IRT and the clinical database, the values recorded in the clinical database will be used for analyses. Given that the study is terminated early, sensitivity analysis of the primary efficacy endpoint will not be performed for the stratification discrepancy.

### **3.4. Data Handling Conventions and Transformations**

Subject age collected at Screening visit will be used for analyses and presented in listings. The age is derived in the electronic data capture (EDC) system based on year of birth and informed consent date.

Laboratory data that are continuous in nature but are less than the lower limit of quantitation (LLOQ), less than the limit of detection (LOD), or above the upper limit of quantitation (LOQ) will be imputed for the purposes of calculating descriptive statistics.

A value that is half of the LLOQ will be used to calculate descriptive statistics if the datum is reported in the form of  $<x$  or  $\leq x$  (where x is considered the LLOQ or LOD), or is reported as not detected. If the LLOQ is reported in log units, the imputed value will be half of the equivalent non-log LLOQ value.

A value that is 1 significant value unit above the upper LOQ will be used to calculate descriptive statistics if the datum is reported in the form of " $>x$ " (where x is considered the LOQ). For example, if the result of a continuous laboratory test is  $>20$ , a value of 21 will be assigned. If the result of a continuous laboratory test is  $>20.1$ , a value of 20.2 will be assigned.

The LOQ will be used to calculate descriptive statistics if the datum is reported in the form of " $\geq x$ " (where x is considered the LOQ).

For selected analyses, virology efficacy data will be transformed to the logarithmic (base 10) scale.

Total bilirubin values entered as  $< 0.2$  mg/dL will be analyzed as 0.1 mg/dL; direct bilirubin values entered as  $< 0.1$  mg/dL will be analyzed as 0.05 mg/dL (according to the methods of Nehls and Akland, 1973).

### **3.5. Missing Data and Outliers**

#### **3.5.1. Missing Data**

In general, missing data will not be imputed unless methods for handling missing data are specified. Exceptions are presented in this document.

For missing last dose date of study drug, imputation rules are described in [Section 4.2.1](#). The handling of missing efficacy data is described in [Section 6.1.2](#). The handling of missing or incomplete dates for adverse event (AE) onset is described in [Section 7.1.5.2](#), and for prior and concomitant medications in [Section 7.4](#).

#### **3.5.2. Outliers**

Outliers will be identified during the data management review process. No sensitivity analyses will be conducted. All data will be included in the data analysis.

### **3.6. Analysis Visit Windows**

#### **3.6.1. Definition of Study Drug**

In this study, study drugs are defined as VBR, ETV, and Peg-IFN $\alpha$ .

#### **3.6.2. Definition of Study Phase**

The following phases will be defined: Randomized Treatment Phase and Overall Treatment Phase are on treatment; and the Follow-up Phase is off treatment.

- Randomized Treatment Phase: from first dose date through Week 24 visit (or premature termination visit if before Week 24)
- Overall Treatment Phase: from first dose date through Week 48 visit (or premature termination visit if before Week 48)
- Follow-up Phase: after Week 48 visit (or premature termination visit) through end of study

End of study will be when the subject completes the last visit of the follow-up period or is considered “lost to follow-up,” whichever is later.

#### **3.6.3. Definition of Study Day**

The first dose date of VBR when administered in combination with ETV with or without Peg-IFN $\alpha$  will be calculated where applicable. Study Day 1 is defined as the first dose date of study drug, which is the earliest/minimum of the first dose dates of VBR, ETV, and Peg-IFN $\alpha$  in a treatment group. If the first dose date is missing, the date of randomization will be used.

The last dose date of VBR, ETV, and of Peg-IFN $\alpha$  will be calculated where applicable. For the Randomized Treatment Phase, the last dose date of study drug VBR will be the Week 24 visit date or the end date on study drug administration CRF if a subject discontinued study drug prior to Week 24 visit. For study drug ETV, the last dose date will be obtained from End of Treatment-ETV eCRF. For study drug Peg-IFN $\alpha$ , the last dose date will be obtained from End of Treatment-Peg-IFN $\alpha$  eCRF. For the Overall Treatment Phase, the last dose date for each drug will be the end date on the respective End of Treatment eCRF pages. The last dose date of study drug will be defined as the latest/maximum of the last dose dates of VBR, ETV, and Peg-IFN $\alpha$  in a treatment group.

For the on-treatment phases, Study Day will be calculated from Study Day 1 and derived as follows:

- For days prior to the first dose: Assessment Date – Study Day 1
- For postdose study days: Assessment Date – Study Day 1 + 1

For the Follow-up Phase, the follow-up Study Day 1 is defined as the day after Week 48 visit or Premature Termination visit. The follow-up study day will be derived as Assessment Date – follow-up Study Day 1 +1.

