### 3.6.4. Analysis Visit Windows

Subject visits might not occur on protocol-specified days. Therefore, for the purpose of analysis, observations will be assigned to analysis windows. In general, the baseline value will be the last nonmissing value on or prior to the first dose date of study drug. The on-treatment phases include Randomized Treatment Phase and Overall Treatment Phase. For the Randomized Treatment Phase, the data will be summarized up to the Week 24 visit or premature termination visit. For the Overall Treatment Phase, the data will be summarized up to the Week 48 visit or premature termination visit. For the Follow-up Phase, the data will be summarized from follow-up Study Day 1 through the end of study, where Follow-Up Baseline data is from Week 48 visit or premature termination visit.

The analysis windows for the on-treatment HBV DNA and HBV pgRNA assessments are provided in Table 3-1.

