### **4.2.1. Duration of Exposure to Study Drug**

Total duration of exposure to each study drug through Week 24 will be defined as the last dose date at Week 24 minus the first dose date plus 1 for VBR and for ETV, plus 7 for Peg-IFN $\alpha$ , regardless of any temporary interruptions in study drug administration, and will be expressed in weeks using up to 1 decimal place (eg, 4.5 weeks). Duration (weeks) = Duration (days) / 7. Total duration of exposure to VBR through Week 48 will also be summarized and defined as the last dose date of VBR minus the first dose date plus 1 for VBR, similar calculation will be performed for total duration of ETV exposure. The last dose date of individual study drug is defined in [Section 3.6.3](#). If the last study drug dose date is missing, the latest date among the study drug end date, clinical visit date, laboratory sample collection date, and vital signs assessment date that occurred during the on-treatment period will be used for subjects included in the final analyses or the last available date in the database snapshot for subjects who were still on treatment at the time of an interim analysis.

The total duration of exposure to study drug will be summarized using descriptive statistics. Summaries will be provided by treatment group in each on-treatment phase for the Safety Analysis Set. For the Randomized Treatment Phase, the expected total duration of Randomized Treatment Phase for all subjects is 24 weeks. The distribution of subjects by the total number of weeks on therapy (ie,  $\leq$ 4 weeks, >4-8 weeks, >8-12 weeks, >12-16 weeks, >16-20 weeks, >20-24 weeks, and  $\geq$ 24 weeks) will be presented. After completion of the randomized treatment, all subjects will receive VBR+ETV for an additional 24 weeks. For the Overall Treatment Phase, the duration of exposure to VBR and ETV will be summarized. The expected total duration of

Overall Treatment Phase for all subjects is 48 weeks. The distribution of subjects by the total number of weeks on therapy (ie,  $\leq 12$  weeks,  $> 12-24$  weeks,  $> 24 - < 48$  weeks, and  $\geq 48$  weeks) will be presented.

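### SAP 3.6.3 sets no Week 24 cap on the ETV last dose date for the Randomized Treatment Phase, and the 1008 expected VBR tablets in SAP 4.2.2.1 do not fit Group 3, which is scheduled for 504

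*Combined protocol and SAP*

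**What the plan says.** **ETV last dose date.** SAP 3.6.3 treats the drugs differently in the Randomized Treatment Phase. VBR ends at the Week 24 visit, or earlier if it was discontinued. For entecavir, "For study drug ETV, the last dose date will be obtained from End of Treatment-ETV eCRF". Peg-IFNα is also taken from its own page. In the later, 48-week phase the rule is that "the last dose date for each drug will be the end date on the respective End of Treatment eCRF pages". Study drug as a whole then ends on the latest of the three drug dates.

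Other sections bound the phase at Week 24. SAP 3.6.2 defines it as "Randomized Treatment Phase: from first dose date through Week 24 visit (or premature termination visit if before Week 24"). SAP 3.6.4 says "For the Randomized Treatment Phase, the data will be summarized up to the Week 24 visit or premature termination visit". SAP 4.2.1 says "Total duration of exposure to each study drug through Week 24 will be defined as the last dose date at Week 24", goes on to name both VBR and ETV in the formula, and adds that "the expected total duration of Randomized Treatment Phase for all subjects is 24 weeks". It also says "The last dose date of individual study drug is defined in" Section 3.6.3.

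**VBR tablets.** SAP 4.2.2.1 gives each subject who completes treatment and receives VBR an expected 504 tablets over 24 weeks and 1008 over 48 weeks, with no exception by group. Its general rule sets the denominator by the subject's actual time on treatment. SAP 1.2 and Protocol 4.1 give Group 3 ETV plus Peg-IFNα to Week 24, and VBR plus ETV only from Week 24 to Week 48.

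**The concern.** For Peg-IFNα an uncapped end-of-treatment page does no harm, because Protocol Appendix 1 (footnote 19) stops it at Week 24. ETV is different: it continues in all groups to Week 48 and then through follow-up to Week 60. One page date serves both phases, so for anyone still on ETV after Week 24 it cannot also be a Week 24 date. SAP 4.2.1 asks for a Week 24 date and points to 3.6.3, which does not supply one.

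The stated VBR denominator has a similar gap. A Group 3 subject who completes treatment does receive VBR, so the sentence covers that subject, yet the protocol never schedules 1008 tablets for that group.

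Followed as written, the ETV exposure table for the randomized phase would not describe that phase, and one arm of three would look non-compliant with VBR by construction. There is also a possible safety consequence. If the uncapped ETV date entered the latest-date rule, Randomized Treatment Phase windows could run past Week 24. Group 3 events arising on VBR could then be counted in the period meant to be free of it.

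**Working it through.** **1. Reproduce the plan's figures.** Inputs are three VBR tablets and one ETV tablet daily (SAP 4.2.2.1).

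- VBR: 3 × 7 × 24 = 504; 3 × 7 × 48 = 1008.
- ETV: 1 × 7 × 24 = 168; 1 × 7 × 48 = 336.

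All four match the SAP, so the arithmetic is correct. The question is to whom and to which period the figures apply.

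**2. ETV exposure, Randomized Treatment Phase.** The formula is (last dose date − first dose date + 1) / 7. Cut at nominal Day 168, it gives 168 / 7 = 24.0 weeks. Let W be the week at which on-treatment dosing stops, from 24 to 48. The eCRF page is not in the documents, so two readings are shown.

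| W | Intended | Page closes at treatment stop | Page holds last follow-up dose, W + 12 (assumption) |
|---|---|---|---|
| 24 | 24 | 24 (+0) | 36 (+12) |
| 36 | 24 | 36 (+12) | 48 (+24) |
| 48 | 24 | 48 (+24; 48/24 = 2.0×) | 60 (+36; 60/24 = 2.5×) |

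The tablet formula in SAP 4.2.2 (dispensed minus returned) states no phase boundary. If ETV tablets were summed to the same uncapped date against the stated 168, a fully adherent completer would score 336/168 = 200%, or 420/168 = 250% on the second reading.

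**3. Latest-date rule.** For a Group 1 completer the randomized-phase dates would be Week 24 for VBR and at least Week 48 for ETV, so the maximum is at least Week 48 instead of Week 24. SAP 7.1.6 and 7.2.1.1 carry their own wording that ends the randomized phase at the Week 24 dose. A programmer may therefore cut correctly, but 3.6.3 does not derive that date for ETV either.

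**4. Group 3 VBR compliance.** Scheduled tablets are 3 × 7 × (48 − 24) = 504.

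- Against the stated 1008: 504/1008 = 50.0%, in the lowest band (80% or less).
- Against the Group 3 schedule: 504/504 = 100%.

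Early stoppers have a separate denominator, the amount expected by the discontinuation date, but the starting point is not stated. For a fully adherent Group 3 subject stopping at Week 36, counting from Week 24 gives 252/252 = 100%, while counting from Day 1 gives 252/756 = 33.3%.

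**5. Boundary day.** If a Group 3 subject's first VBR dose is taken at the Week 24 visit on Day 168, counting inclusively to Day 336 gives 336 − 168 + 1 = 169 days and 169 × 3 = 507 tablets, with 3 of them falling in the Randomized Treatment Phase. A corrected denominator must assign that day to one phase only.

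**The case against.** The best defence on ETV is that the governing formula already contains the cut-off. SAP 4.2.1 speaks of exposure through Week 24, uses the last dose date at Week 24, and names ETV. SAP 4.2.2.1 fixes 168 ETV tablets for the phase, and 3.6.2 and 3.6.4 end it at the Week 24 visit. A 48-week result means ignoring those words. This stands as evidence of intent, and it is why the point is minor. It does not supply the date: 4.2.1 sends the reader to 3.6.3, whose ETV sentence has no cap.

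On VBR, the defence is that 1008 is tied to a 48-week period, that SAP 4.2 measures compliance against the protocol regimen, and that the on-treatment rule gives 504 for Group 3. This is a fair reading. However, the section does not say that the on-treatment period is drug-specific, and SAP 3.6.2 starts the on-treatment phases at the first dose date without tying it to one drug. The missing Group 3 qualifier is therefore a real gap. It is a matter of scope, and 1008 is not a miscalculation.

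A reader might also infer that Overall Treatment Phase ETV exposure is inflated by about 12 weeks. The documents do not support that as a finding. ETV continues in follow-up with final accountability at Week 60, but SAP 3.6.2 says "the Follow-up Phase is off treatment", so the page may close at treatment stop, in which case the excess is zero.

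**Conclusion.** Both rules give a wrong result if followed literally, and both conflict with the SAP's own intent. For a completer, Randomized Treatment Phase ETV exposure computes as at least 48 weeks instead of 24. This assumes that the ETV page carries one end date covering the whole of on-treatment dosing. The 60-week figure (2.5×) needs the further assumption that the page records the last follow-up dose, which the documents do not show, so it is only an upper case. For subjects whose treatment ended between Weeks 24 and 48, the excess on the first reading is 0 to 24 weeks.

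A fully adherent Group 3 completer scores 50% instead of 100% on the stated denominator. Group 3 was planned at about 60/3 = 20 subjects; the number of completers is unknown because of the early termination.

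Exposure and compliance tables are directly affected. It would be too narrow to say that nothing else can move, because the ETV date enters the latest-date rule, and adverse events and laboratory results belong to the primary endpoint. It would be too strong to infer that the primary safety results are wrong: 7.1.6 and 7.2.1.1 have their own Week 24 wording, so an error there is possible but not shown. No efficacy result changes. Severity is minor.

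**What to change.** **(a) SAP 3.6.3.** State that, for the Randomized Treatment Phase, the ETV last dose date is the earlier of the Week 24 visit date and the recorded ETV end date, or the premature termination visit if that falls before Week 24. Use this capped date wherever the phase's last dose date is used, including the maximum across the three drugs. In SAP 4.2.2, count ETV tablets for the phase to the same date where visit-level accountability is available.

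**(b) SAP 4.2.2.1.** Give the completer VBR denominators by randomized group:

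| Group | Randomized Treatment Phase | Overall Treatment Phase |
|---|---|---|
| 1 and 2 | 504 | 1008 |
| 3 | not applicable | 504 |

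Add that Group 3 expected tablets are counted from the start of VBR after the randomized phase, and that the Week 24 visit day belongs to one phase only.

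**Cost.** The change needs SAP wording and derivation code. The inputs are largely in hand: Protocol 6.4 has drug counted at each visit after Day 1. Some visit-level counts may be missing, because forgotten returns are brought to the next visit and accountability at the Premature Termination Visit (Protocol 7.9) is required only if applicable. SAP Section 1 already provides for changes made after finalization to be documented in the Synoptic CSR.
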